7.2.3 Withdrawal of Patients

Patients/caregivers will be informed that they have the right to withdraw from the study at any time, without prejudice to their medical care, and that they are not obliged to state their reasons.

Any withdrawal, and reasons for withdrawal, must be fully documented in the eCRF and source documents and the patient followed by the investigator/investigative staff. Withdrawn patients will not be replaced.

Patients will be withdrawn in the following circumstances:

- A patient's/caregiver's desire for withdrawal for any reason
- Lost to follow-up (every effort must be made to contact the patient/caregiver; a certified letter must be sent)
- An AE which, in the opinion of the investigator, necessitates withdrawal
- Death
- A patient's/caregiver's substantial non-compliance (eDiary and study drug compliance) or protocol violation
- An investigator's opinion that continuing the patient in the study is not appropriate. The investigator may withdraw a patient at any time, if it is considered to be in the patient's best interest
- Liver transplantation

The reason and the date the patient is withdrawn from the study will be documented in the eCRF and source documents. If a patient is withdrawn from further treatment with the study

drug, the investigator/investigative staff will attempt to complete all Visit 11 procedures at the time the patient is prematurely withdrawn from the study. The investigator/investigative staff will also attempt to complete all Visit 12 procedures 28 days following premature withdrawal (i.e., 28 days following the final dose of the study drug).

If a patient discontinues prior to Week 72, additional telephone contacts will be made every 3 months after the Follow-up Visit (Visit 12) up to Week 72 to gather whether or not the patient has had biliary diversion or liver transplantation, and of ongoing TEAEs at the time of discontinuation have resolved. The telephone calls will take place up until 72 weeks even if the patient has biliary diversion or liver transplant.

7.2.4 Study Termination by Sponsor

This study may be terminated at any time by Albireo if significant safety concerns develop or, in the sponsor's judgment, there are no further benefits to be achieved from continuation of the study. In this event, Albireo/designee will inform the study investigators, institutions and all regulatory authorities.

Albireo may temporarily or permanently discontinue the study at an investigative site at any time for safety, ethical, compliance or other reasons. If this is necessary, Albireo will endeavor to provide advance notification to the site. If a site or the study is suspended or discontinued, the investigator/investigative staff will be responsible for promptly informing the Independent Ethics Committee (IEC)/Institutional Review Board (IRB) that this has happened. If required by local regulations, Albireo/designee will be responsible for informing the IEC/IRB and the Regulatory Authority of study or site discontinuation. In such an event, all study data and unused study drug must be returned to Albireo.

8 TREATMENT OF PATIENTS

8.1 Identity of Study Drug

A4250 will be supplied as capsules for oral administration. White opaque capsules filled with pellets containing A4250 will be provided. Two different capsule sizes will be available:

- Capsule size 0 that can be opened
- Capsule size 3 that should be swallowed intact. The size 3 capsules may be opened only under exceptional circumstances, e.g., patient cannot swallow the capsule intact.

Bottles with 34 capsules will be given to the patient at each visit. A patient who requires 2 or more capsules per day will be given multiple bottles. Refer to the Investigational Product Manual.

A 5-digit study drug number will identify study drug packs and will be detailed on the study drug label. Dispensing of study drug will be coordinated by the Interactive Web Response System (IWRS). The system will assign study drug number(s) using a packing list based on the patient's weight and dose level (either 120 µg/kg/day or 40 µg/kg/day) for dispensation at each dispensing visit. In case of technical issues accessing the system online, please see the IWRS site user manual for country-specific contact telephone numbers to the ICON HelpDesk 24/7 system support.

8.2 Administration of Study Drug

Patients will be dosed with 120 µg/kg/day or 40 µg/kg/day⁴ for 72 weeks or 40 µg/kg/day for the first 12 weeks followed by 120 µg/kg/day for the remaining 60 weeks⁴. Patients not tolerating the 120 µg/kg/day dose after a minimum of 1 week, for reasons other than new liver findings and severe diarrhea, will have the option to down-titrate to a lower dose (40 µg/kg/day). They should return to the higher dose as soon as deemed appropriate by the investigator. More than one upward dose titration (from 40 µg/kg/day directly to 120 µg/kg/day) for the same event is not recommended. If, in the opinion of the investigator, a dose titration should be considered prior to the 1 week minimum, the investigator should consult with the Medical Monitor or designee. Any dose titration should be done in consultation with the sponsor Medical Monitor or designee.

Study drug will be dispensed to the patient at defined intervals from Visit 1 through Visit 9, together with instructions on how to store and take the drug. Study drug administration data, including whether each patient took each dose or partial doses of study drug, whether there were any delayed or missed doses, and whether the capsule was opened or swallowed whole, will be documented through the diaries and transferred to the study database.

⁴ As of Protocol Amendment 6.2 Sweden patients entering Cohort 2 will start treatment at 40 µg/kg/day with the possibility to dose escalate to 120 µg/kg/day after 12 weeks if there is no improvement in pruritus based on investigator judgment.

A4250 should be taken in the morning together with food. On clinic visits days when laboratory assessments are conducted (Visits 1 to 10), study drug should be taken after the visit. Patients should not crush or chew the capsule(s). When swallowing the capsule intact, the patient should administer the dose with a glass of water.

If the study medicine needs to be mixed in a small amount of food because the patient is unable to swallow the capsule intact, the capsule can be twisted open and the contents sprinkled and mixed in a small amount (one or two tablespoons (15 to 30 mL)) of room-temperature yogurt, apple sauce, oatmeal, or fruit purée. If the patient has not yet been weaned onto solid foods, the capsule contents can be sprinkled into a small amount (a few milliliters) of water, baby formula or breast milk and administered with an oral dosing pipette. Please see Pharmacy manual for detailed instructions.

If a patient's weight changes at any time during the study, dose adjustment will be required. The number of capsules provided to the patient should be based on the body weight thresholds identified in [Table 2](#).

Table 2 Dosing and Capsule Strength

Body Weight (kg)	Capsule Size	Number of Capsules per Day ^{a,b}	Capsule Strength, Low Dose ^a (µg)	Total Dose (µg) ^a	Capsule Strength, High Dose ^b (µg)	Total Dose (µg) ^b
5 to <7.5	0	1	200	200	600	600
7.5 to <12.5	0	2	200	400	600	1200
12.5 to <17.5	0	3	200	600	600	1800
17.5 to <19.5	0	4	200	800	600	2400
19.5 to <25.5	3	2	400	800	1200	2400
25.5 to <35.5	3	3	400	1200	1200	3600
35.5 to <45.5	3	4	400	1600	1200	4800
45.5 to 55.5	3	5	400	2000	1200	6000
>55.5	3	6	400	2400	1200	7200

a Low dose: 40 µg/kg/day

b High dose: 120 µg/kg/day

8.3 Study Drug Packaging and Labelling

8.3.1 Packaging and Labelling

The capsules will be packed in high-density polyethylene containers, with childproof polypropylene caps. Study drug capsules containing A4250 in the strength specified in the table above will be manufactured.

Packaging and labelling will be prepared to comply with applicable regulatory requirements.

8.3.2 Storage

Treatment packs containing A4250 capsules should be stored and dispensed in accordance with regulations in their original containers. The storage facility at the investigative site should be locked and storage should be between 15°C and 25°C.

Patients/caregivers should be informed of appropriate storage conditions (i.e., room temperature, between 15°C and 25°C).

Any deviations from the recommended storage conditions should be immediately reported to Albireo and the study drug should not be used until authorization has been given by Albireo.

8.3.3 Blinding and Randomization of Study Drug

Not applicable.

8.4 Procedure for Breaking the Randomization Code

Not applicable.

8.5 Patient Compliance

The study nurse will monitor eDiary compliance by routine review of the CRF Health website. Patient/caregivers will be instructed to fill in the eDiary every morning and evening for the first 24 weeks and the last 21 days before all the remaining visits to the clinic. There will be no interruption between Visits 11 and 12. If both diary entries on a day are missing during this time, the study nurse will call the caregiver/patient to remind them to complete all scheduled entries. Any non-compliance will be documented and explained in the source documents.

Study drug compliance will be assessed by review of returned unused medication and by counting returned capsules at Visits 2 through 11, inclusive. Study drug compliance will be calculated for each patient and listed.

Treatment Compliance = $100 \times ((\text{Number of study drug dispensed} - \text{number of study drug returned}) / \text{number of study drug that should be taken})$

Treatment compliance between 80% and 120% will be acceptable.

8.6 Patient Identification

After written informed consent is obtained from an eligible patient, an 8-digit patient identification number will be assigned. The first 2 digits will denote the country, followed by a 3-digit site number and a 3-digit patient sequence number. This number will be captured by the IWRS, when the patient first enters the system in A4250-008. Cohort 1 patients will be assigned the same patient number as used in the A4250-005 study, while Cohort 2 patients will be assigned a new unique patient number.

8.7 Study Drug Accountability

Records shall be maintained of the delivery of study treatment to the study site(s), the inventory at the study site(s), the use of each patient and the return to Albireo.

These records shall include dates, quantities, batch numbers, expiry dates and the unique code numbers assigned to the study drug and to the study patients.

The investigator will be responsible for ensuring that the records adequately document that the patients were provided the quantities specified in the protocol and that all study drug received from Albireo is reconciled.

8.8 Concomitant Therapy and Prohibited Medications

For Cohort 1 patients, the investigator will note all ongoing medication in the eCRF at Visit 1. For Cohort 2 patients, the investigator will note all ongoing medication and any medication recently stopped (within 1 month prior to Visit S-1) in the eCRF at Visit S-1. At Visits 2 to 12, (and S-2 for Cohort 2) all changes in medication (stopping or starting new medication or changes in dose) will be recorded in the eCRF. All medication (prescribed or over the counter) for pruritus, sleep, and vitamin supplementation will be recorded.

All medications still being taken by a patient on or after first intake of study drug and which continue to be taken during the study are regarded as concomitant medication.

The protocol allows for patients to be vaccinated against COVID-19 while in the study, based on the treating physician's clinical assessment of the risks and benefits of study participation. Therefore, the COVID-19 vaccine can be administered as a concomitant medication. The date of COVID-19 vaccination must be recorded in the clinical database if administered during study participation.

Concomitant medication guidelines are listed in [Appendix 1](#).

9 ASSESSMENT OF EFFICACY

9.1 Efficacy Endpoints

9.1.1 Primary Efficacy Endpoints

The primary efficacy endpoints are:

EU and rest of world: Change from baseline in serum bile acids after 72 weeks of treatment.

US: Proportion of positive pruritus assessments at the patient level over the 72-week treatment period using the Albireo ObsRO instrument.

9.1.2 Secondary Efficacy Endpoints

EU and rest of world: Proportion of positive pruritus assessments at the patient level over the 72-week treatment period using the Albireo ObsRO instrument.

US: Change from baseline in serum bile acids after 72 weeks of treatment.

All Regions:

- Change from baseline in serum bile acids at Weeks 4, 12, 22, 24, 36, 46, 48, 60, 70, 72, and 76
- Proportion of individual assessments meeting the definition of a positive pruritus assessment at the patient level using the Albireo ObsRO instrument from Weeks 0-4, Weeks 0-12, Weeks 0-22, Weeks 0-24, Weeks 0-36, Weeks 0-46, Weeks 0-48, Weeks 0-60, and Weeks 0-70, respectively, or the proportion of positive pruritus assessments at each 4-week interval between Visit 1/Screening and Visit 5/Week 24, then by each visit between Visit 5/Week 24 to Visit 12/Week 76
- Proportion of individual AM assessments meeting the definition of a positive pruritus assessment at the patient level using the Albireo ObsRO instrument from Weeks 0-4, Weeks 0-12, Weeks 0-22, Weeks 0-24, Weeks 0-36, Weeks 0-46, Weeks 0-48, Weeks 0-60, Weeks 0-70, and Weeks 0-72, respectively, or the proportion of positive pruritus assessments at each 4-week interval between Visit 1/Screening and Visit 5/Week 24, then by each visit between Visit 5/Week 24 to Visit 12/Week 76
- Proportion of individual PM assessments meeting the definition of a positive pruritus assessment at the patient level using the Albireo ObsRO instrument from Weeks 0-4, Weeks 0-12, Weeks 0-22, Weeks 0-24, Weeks 0-36, Weeks 0-46, Weeks 0-48, Weeks 0-60, Weeks 0-70, and Weeks 0-72, respectively, or the proportion of positive pruritus assessments at each 4-week interval between Visit 1/Screening and Visit 5/Week 24, then by each visit between Visit 5/Week 24 to Visit 12/Week 76
- All-cause mortality, number of patients undergoing biliary diversion surgery or liver transplantation. These parameters will be evaluated separately and together at weeks 24, 48, and 72

- Change in growth from baseline to Weeks 24, 48, and 72 after initiation of A4250 treatment, defined as the linear growth deficit (height/length for age, weight for age, mid-arm circumference, and body mass index [BMI]) compared to the standard growth curve (Z-score, standard deviation [SD] from P50)
- Change in AST to platelet ratio index (APRI) score and Fib-4 score from baseline to Week 72
- Change in pediatric end-stage liver disease (PELD)/model for end-stage liver disease (MELD) score from baseline to Week 72
- Change in use of antipruritic medication at Weeks 24, 48, and 72

9.1.3 Exploratory Efficacy Endpoints

All Exploratory Endpoints will be evaluated at Weeks 24, 48, and 72 unless otherwise noted. Baseline is calculated prior to initiation of A4250 treatment. Exploratory endpoints include:

- Change in serum ALT, GGT, and total bilirubin concentration from baseline to Week 72
- Proportion of individual assessments meeting the definition of a positive pruritus assessment at the patient level over the 72-week Treatment Period. A positive pruritus assessment includes an itch score ≤ 1 , or at least a one-point drop from baseline based on the Albireo PRO instrument; only patients ≥ 8 years of age will complete the Albireo PRO instrument
- Change from baseline over the 72-week treatment period in sleep parameters measured with the Albireo PRO and ObsRO instruments
- Change from baseline in INR, albumin, liver enzymes, leukocytes, and platelets
- Change from baseline measures of bile acid synthesis (autotaxin, p-C4)
- Assessment of Global Symptom Relief at Weeks 4, 12, 24, 48, and 72 as measured by patient, caregiver, and clinician PGIC items
- Change from baseline by each 4-week interval between Visit 1/Screening and Visit 5/Week 24, then by each visit between Visit 5/Week 24 to Visit 12/Week 76 in patient-reported and observer-reported night time itching and scratching severity scores, respectively
- Change from baseline by each 4-week interval between Visit 1/Screening and Visit 5/Week 24, then by each visit between Visit 5/Week 24 to Visit 12/Week 76 in patient-reported and observer-reported morning time itching and scratching severity scores, respectively
- Change from baseline by each 4-week interval between Visit 1/Screening and Visit 5/Week 24, then by each visit between Visit 5/Week 24 to Visit 12/Week 76 in pooled pruritus score including observer-reported scratching for patients < 8 years of age and patient-reported itch severity for patients ≥ 8 years of age

- Change from baseline by each 4-week interval between Visit 1/Screening and Visit 5/Week 24, then by each visit between Visit 5/Week 24 to Visit 12/Week 76 in additional patient-reported and observer-reported sleep parameters (e.g., tiredness, number of awakenings)
- Change from baseline in PedsQL questionnaire
- Change from baseline in stage of liver fibrosis as assessed by Fibroscan® (where available)
- Change from baseline in stage of liver fibrosis as assessed by post-treatment biopsy (when available)

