Methodology: This is a Phase 3, multi-center, open-label extension study to investigate the long-term efficacy and safety of a 120 µg/kg/day daily dose of A4250 in patients with PFIC, including episodic forms also referred to as benign recurrent intrahepatic cholestasis (BRIC). Cohort 1 will consist of children with PFIC Types 1 and 2 who have participated in study A4250-005. Cohort 2 will consist of approximately 60 patients with PFIC who have elevated serum bile acids and cholestatic pruritus and who either (1) do not meet eligibility criteria for Study A4250-005 (PEDFIC 1) or (2) are eligible for enrolment in A4250-005 after recruitment of study A4250-005 has been completed. Up to 40 patients post biliary diversion surgery are allowed to participate in Cohort 2. Eligible patients will be enrolled into this open-label extension study and treated with a daily dose of 40 µg/kg/day ¹ or 120 µg/kg/day of A4250 for 72 weeks, or 40 µg/kg/day for the first 12 weeks followed by 120 µg/kg/day for the remaining 60 weeks ¹ . Patients not tolerating the 120 µg/kg/day dose after a minimum of 1 week will have the option to down-titrate to a lower dose (40 µg/kg/day). The patient should return to the higher dose as soon as deemed appropriate by the investigator. More than one upward dose titration (from 40 µg/kg/day directly to 120 µg/kg/day) for the same event is not recommended. Any dose titration should be done in consultation with the sponsor Medical Monitor or designee.				

¹ As of Protocol Amendment 6.2 Sweden, patients entering Cohort 2 will start treatment at 40 µg/kg/day with the possibility to dose escalate to 120 µg/kg/day after 12 weeks if there is no improvement in pruritus based on investigator judgment.

Name of Sponsor/Company:	Name of Product:	Name of Active Ingredient:
Albireo AB	A4250	A4250
Number of Patients:		
Approximately 120 patients in total. Approximately 60 patients will be enrolled following participation in Study A4250-005 (Cohort 1) and approximately 60 patients will be enrolled directly into this study (Cohort 2).		
Diagnosis and Main Criteria for Inclusion:		
Cohort 1:		

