9.2.8 Fibroscan®

Where available, Fibroscan® will be performed as per institution standard practice at Visits 1, 5, 8, and 11.

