11.2.2.2 Missing Data

Missing data will be reported descriptively. In general, imputations of missing observations will not be made. Any additional sensitivity analysis concerning missingness and details regarding handling of missing data will be described in the statistical analysis plan (SAP).

Continued collection of efficacy data for patients who discontinue treatment will be made as far as possible.

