11.2.2.6 Evaluation of Secondary and Exploratory Efficacy Variables

All secondary and exploratory variables listed under [Sections 9.1.2](#) and [9.1.3](#) will be analyzed descriptively for categorical and continuous data, as applicable. For continuous data, the change from baseline will be analyzed in addition to the actual visit values. For categorical data, shift tables or frequency and percentages of patients will be presented as appropriate.

Change in growth (Z-score, SD from P50 standard growth curve) will be analyzed by using one-sample T-test or Wilcoxon signed-rank test as appropriate. Change in growth (height/length for age, weight for age, BMI, and mid-arm circumference) will also be displayed using graphical presentations.

A 95% CI will be calculated for the proportion of patients experiencing surgical bile diversion or liver transplantation or death as well as for the proportion of patients experiencing surgical bile diversion or death or liver transplantation. The upper boundary will be compared to the expected proportion of events, using the event probability estimated from the untreated reference population in an ongoing observational cohort study.

Time to first event, i.e., time to surgical bile diversion or liver transplantation or death, will be explored by descriptive statistics and Kaplan-Meier curves, which also will be used to make a comparison to the NAPPED population. The propensity score matched cohort analysis using inverse probability of treatment weights will be used to match the study patient population to the reference population based on age group and PFIC type.

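### The Fibroscan exploratory endpoint is fixed as change in fibrosis stage, which drops all within-stage change and rests on cut-offs that the protocol does not state

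*Protocol*

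**What the plan says.** Section 9.1.3 lists as an exploratory endpoint "Change from baseline in stage of liver fibrosis as assessed by Fibroscan® (where available". The synopsis (Section 2) has the same wording in both the Sweden-specific and the UK-specific version. The next item in Section 9.1.3 is the parallel biopsy endpoint, "Change from baseline in stage of liver fibrosis as assessed by post-treatment biopsy (when available".

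On the measurement, Section 9.2.8 says only: "Where available, Fibroscan® will be performed as per institution standard practice at Visits 1, 5, 8, and 11". Visits 5, 8 and 11 are Weeks 24, 48 and 72. The supplied text names no stiffness variable, no unit, no stage cut-offs and no central reading.

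Section 11.2.2.6 applies its rules to the variables as listed in Sections 9.1.2 and 9.1.3. One rule is "For categorical data, shift tables or frequency and percentages of patients will be presented as appropriate". The other is "For continuous data, the change from baseline will be analyzed in addition to the actual visit values". Section 11.2.2.2 adds: "In general, imputations of missing observations will not be made".

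The other non-invasive fibrosis markers, APRI and Fib-4, are secondary endpoints analysed as change in score (Section 9.1.2), with formulas and visits in Section 9.2.9.

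**The concern.** The premise, which the protocol does not spell out, is that Fibroscan returns a continuous stiffness reading and that a stage exists only after the reading is cut at thresholds. Biopsy is different, because there the stage is what the pathologist reads. For Fibroscan, staging is an extra step that removes information already collected.

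Three things follow.

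- A child whose stiffness falls clearly but stays between two cut-offs is tabulated as unchanged.
- A child whose reading moves slightly across a cut-off is tabulated as a full stage better or worse.
- Without a common set of cut-offs, and with scans done by local practice, the same reading may be given different stages at different sites.

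This is a choice the protocol states, not a detail it leaves open. Because the listed variable is a stage, the categorical rule in Section 11.2.2.6 applies, and the continuous rule has no stiffness variable to act on. What is at stake is how informative one exploratory table is.

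**Working it through.** **1. Is there a plan figure to reproduce?** No. The protocol gives no sample size, expected effect, SD or number of patients for Fibroscan. The only related figure is the total, "Approximately 120 patients in total", which is an upper bound. Everything numerical below is assumed.

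**2. What staging does to single readings.** Take illustrative cut points of 5.5, 7, 9.5 and 12.5.

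| Baseline | Follow-up | Relative change | Change in stage |
|---|---|---|---|
| 9.4 | 7.1 | (7.1 − 9.4)/9.4 = −24% | none |
| 7.1 | 6.9 | (6.9 − 7.1)/7.1 = −3% | one stage better |

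Now suppose a second site uses only 7, 9.5 and 12.5. A fall from 6.0 to 5.0 is one stage better at the first site and no change at the second.

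**3. Size if a paired test were run (illustration).** The inputs are all assumed.

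- SD of within-patient change in log stiffness: 0.35.
- Baseline median: 6, 8, 10 or 14. Between-patient SD on the log scale: 0.3 or 0.5.
- Cut points: the four above, or the last three of them.
- n = 30 or 60, with 4,000 simulated trials per setting and a two-sided 5% paired t-test.
- Equal spread at both visits. This fixes the correlation at 1 − 0.35²/(2·SD²), which is 1 − 0.1225/0.18 = 0.319 for SD 0.3 and 1 − 0.1225/0.50 = 0.755 for SD 0.5.
- A mean fall giving about 80% power on the continuous scale: 0.529 × 0.35 = 0.185 log units at n = 30 (about 17%), and 0.368 × 0.35 = 0.129 at n = 60 (about 12%).

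Power on change in stage at n = 30, against about 80% for the continuous reading:

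| Baseline median | SD 0.3, four cuts | SD 0.3, three cuts | SD 0.5, four cuts | SD 0.5, three cuts |
|---|---|---|---|---|
| 6 | 65% | 42% | 57% | 43% |
| 8 | 74% | 68% | 65% | 57% |
| 10 | 74% | 72% | 67% | 61% |
| 14 | 64% | 64% | 56% | 55% |

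At n = 60 the range is 45% to 75%. Over both sample sizes and repeated runs, stage power is about 41% to 76%. The loss is about 5 to 39 points, and 29% to 68% of patients show no change in stage.

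**4. A second measure, with different assumptions.** Relative efficiency is [(mean/SD) of stage change ÷ (mean/SD) of continuous change]². Baseline is standard normal, the mean change is −0.1 to −0.5 and its SD is 0.3 or 0.5, all in baseline SD units.

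| Cut-offs | Relative efficiency | No change in stage |
|---|---|---|
| Five equal-probability stages | 0.33 to 0.60 | 45% to 68% |
| Four equal-probability stages | 0.26 to 0.51 | 53% to 75% |
| Five stages, cut-offs all above the baseline median | 0.14 or less | 75% to 83% |

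The last row should be read with care. Spread widens slightly in this model, and with one-sided cut-offs that alone raises the mean stage.

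**5. Sensitivity to the model.** If the spread of stiffness in step 3 is allowed to widen over time, stage change appears more powerful than the reading in some settings. That gain is false. With no true shift in log stiffness, the test on stage rejects in up to 56% of trials, against about 5% for the continuous test, because the lowest and highest stages distort the mean.

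**The case against.** The strongest reply is that there is no Fibroscan test to lose power. Section 11.1 says the study has no formal hypothesis testing, and Section 11.2.2.6 makes secondary and exploratory variables descriptive. One-sample tests are named only for bile acids (Section 11.2.2.5) and growth. This stands: the power figures show scale and do not describe a planned analysis. A reader might infer that staging costs well over 5 points in any setting, or that a real improvement is likely to be reported as no change. The documents support neither. They give no expected effect or cut-offs, the smallest loss found was about 5 points, and the sign depends on the model.

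A reader might also infer that the Fibroscan group is small. The protocol says only that scans are done where available, and it gives no number.

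Fibrosis is already followed on continuous scales at a higher tier through APRI and Fib-4, with no availability limit. This also stands, and it lowers the consequence.

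A common stage scale lets Fibroscan be read beside biopsy. That is a fair reason to keep a stage table, but not to make it the only Fibroscan result.

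An analysis plan could add the readings, and Section 9.2.8 does not say that only the stage is recorded. Both are true, so it should not be claimed that the readings will be lost. Even so, the plan would be adding a variable that the protocol does not name.

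Finally, using the reading removes the dependence on local cut-offs but does not standardise how scans are acquired. That limit remains.

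**Conclusion.** The point holds as a minor one. The protocol fixes stage as the Fibroscan variable in Section 9.1.3 and in both synopses. By construction a stage records none of the change within a stage and overstates small changes across a threshold. Comparability between sites rests on cut-offs that are not stated.

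The size cannot be taken from the documents. Under the assumptions listed (illustrative cut points, SD of change 0.35 log units, equal spread at both visits), a paired test would lose about 5 to 39 points from 80% power. Other assumptions give other values. That staging discards information rests only on the premise that a Fibroscan stage is a thresholded continuous reading. No primary, secondary or safety conclusion is affected.

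**What to change.** In Section 9.1.3 and the synopsis, in both country versions, define the endpoint as change from baseline in liver stiffness measured by Fibroscan, where available, at Weeks 24, 48 and 72. Summarise it on the log scale as percent change with a 95% CI, and report the number of patients with paired scans. State that the reading itself is recorded in the eCRF. Keep a stage shift table as supportive, derived from the readings with one common set of cut-offs named in advance. Leave the biopsy stage endpoint as it is.

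The cost is a line of text in each place, one eCRF field if it is not already there, and one table. No visit or procedure is added, because the scans at Visits 1, 5, 8 and 11 already produce the value.
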